5.3 N/A

## 6.0 Procedures Involved

- 6.1 This will be a single-center non-randomized trial that will add to our institution's current diagnostic algorithm one CEUS to subjects whom are clinically suspicious for acute appendicitis. Currently, a gray-scale abdominal ultrasound is performed to help establish the diagnosis. When the results of the gray-scale abdominal ultrasound are inconclusive, the treating physician may choose to refer the patient for a CT scan in order to establish a definitive diagnosis. Our study does not look to alter that process.
- 6.2 For those who consent to study participation, we propose obtaining a CEUS after the initial gray-scale ultrasound. Once the initial ultrasound is complete, the contrast Lumason® (sulfur hexafluoride lipid type-A microspheres) will be administered through an already existing IV catheter by an MD, RN or a radiology technologist trained and certified to administer the Lumason® contrast agent, and

an abdominal scan will be completed. The patient will then continue with standard of care treatment per his treating physician. The CEUS image will be read at a future time by a CMH radiologist blinded to the results of the gray scale ultrasound and CT if one was obtained as these will be used for comparison.

6.3

- Lumason will be administered by radiology personnel (radiologist, US technologist, or Sedation RN). Subjects will be monitored during the entirety of the procedure. Once the study procedure has been completed, patients will continue to go through the standard of care process and return to the ED (Emergency Department) or floor while they await the results of their gray-scale ultrasound and CT, if one was obtained. ED/ floor staff will continue to monitor patients for any adverse events.
- Lumason (sulfur hexafluoride lipid-type A microspheres) is the investigational product. The recommended dose of Lumason for children is 0.03 mL/kg up to a maximum dose of 2.4mL injected into a peripheral intravenous catheter. See individualization of dose below.

1. Follow the Lumason injection with a flush of 5 ml of 0.9% Sodium Chloride Injection, USP.
2. The maximum total dose for children as listed in the package insert should not exceed 2.4 mL in any 10-minute period. For this study, over any 10-minute period we intend to administer the approved dose of 0.03 mL/kg up to a maximum of 2.4 mL.
3. The maximum total dose for children as listed in the package insert should not exceed 4.8 mL in any one patient during the full time on study. In this study, we intend to administer a total dose in any one patient during the full time on study of 0.06 mL/kg with a maximal dose of 4.8 mL.

6.4 Data extracted from the electronic medical record will be entered into a secure REDCap database and stored in a password protected file on the CMH network. A master list containing only the assigned study ID and linking MRN will be kept in a separate REDCap instrument. All electronic files will be kept on the secure password-protected computers of the research staff and principal investigator.

Data points to be collected include the following: demographics, findings on radiology imaging (US, CEUS, and CT if applicable),

pathology, intraoperative findings, other/ comments. Reports of headache, nausea, altered taste, injection site reaction, feeling hot/ flushed, chest pain, or dizziness will also be recorded.

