## 17.0 Risks to Subjects

17.1 As part of SOC, all patients enrolling in this study will have at least one functioning intravenous catheter placed during the SOC blood draw, hence no new IV access will be required. We expect that there may be some mild discomfort related to the performance of the ultrasound study itself and will monitor for this. Other than the discomfort from the ultrasound probe, we do not expect any other ultrasound-related discomfort. Patients will be monitored by licensed personnel during the study interval. Per standard of care, patients will return to the ED while the results of their gray scale ultrasound and CT, if one was taken, are obtained. ED staff will continue to monitor patients for any adverse event.

Reported risks related to Lumason administration include:

Adverse Reaction	Number	(%)
Any Adverse Reaction	340	5
Headache	65	1
Nausea	37	0.5
Dysgeusia	29	0.4
Injection site pain	23	0.3
Feeling hot	18	0.3
Chest discomfort	17	0.2
Chest pain	12	0.2
Dizziness	11	0.2
Injection site warmth	11	0.2

Serious cardiopulmonary reactions, including fatalities, have occurred uncommonly in adults during or shortly following administration of ultrasound contrast agents, including Lumason. These reactions typically occurred within 30 minutes of administration. Hypersensitivity reactions such as skin erythema, rash, urticaria, flushing, throat tightness, dyspnea, or anaphylactic shock have uncommonly been observed following the injection of Lumason. The exclusion criteria eliminate any subjects with a known cardiac abnormality or a known sensitivity to sulfur hexafluoride, so we do not anticipate that these reactions will occur. Resuscitation personnel and equipment will be available during the study treatment and follow-up period.

17.2 This study poses a minor increase over minimal risk as Lumason will be used off-label, but the intervention presents an experience that is reasonably commensurate with those inherent to the subject's medical situation. The only risks attributable to the study are those

of the adverse reactions listed above, as these patients will have already had an IV placed, and would have ultrasound as part of their appendicitis workup. Furthermore, Lumason is currently FDA approved, and in use at CMH, for other abdominal CEUS applications such liver lesions and vesicoureteral reflux in pediatrics.

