17.3 N/A

17.4 N/A

17.5 N/A

## 18.0 Potential Benefits to Subjects

18.1 There is some possibility of potential benefit to subjects participating in this research. Although Lumason is not yet approved for use in diagnosing appendicitis, it is possible that the improved quality of US images produced will provide better information to providers treating these patients. It is also possible that the improved quality imaging could result in incidental findings, such as abdominal anomalies other than appendicitis. If such anomalies are found, the investigator could recommend to parents to follow up with appropriate services.

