## 20.0 Data Management and Confidentiality

20.1 The captured CEUS images will be evaluated by a single Children's Mercy Hospital pediatric radiologist to determine and establish a pattern compared to the standard gray scale ultrasound report. This radiologist will be blinded to the final reads from the gray scale reports. For the children who meet the criteria of appendicitis, they will be followed post-operatively to confirm and correlate the intra-operative findings with the gray scale read.

Descriptive analysis of demographics and patient-level data will be performed using STATA. Direct comparisons will be made with parametric or nonparametric measures depending on the distribution of the data.

- 20.2 This study will be made up of a convenience sampling of children presenting to the CMH Adele Hall emergency department with concerns for appendicitis. Enrollment will consist of up to 250 participants.
- 20.3 All data will be entered into a REDCap database that is accessible only to researchers named on the study. Data will be stored on the CMH secure network. The list of chart identifiers which meet inclusion criteria along with dates of birth will be maintained separately from data that will be used for analysis. Each chart will be reviewed by research staff and data entered directly into the research records. The researchers alone will have full access to the data; we will assign a study ID to the medical records in order that we can reference our information during the course of our research. A master list linking Study ID to MRN, Name and other identifiers will be kept separately from the study data, and accessible only to the study team.
- 20.4 N/A
- 20.5 All data will be entered into a REDCap database that is accessible only to researchers named on the study. Data will be stored on the CMH secure network. The list of chart identifiers which meet inclusion criteria along with dates of birth will be maintained separately from data that will be used for analysis. Each chart will be reviewed by research staff and data entered directly into the research records. The researchers alone will have full access to the data; we will assign a study ID to the medical records in order that we can reference our information during the course of our research. A master list linking Study ID to MRN and other identifiers will be kept separately from the study data, and accessible only to the study team.

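### The gray-scale read, which is the comparator, is not protected from sight of the CEUS images: blinding is specified in one direction only

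*Protocol*

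**What the plan says.** **Order of events.** Protocol section 6.2: "Once the initial ultrasound is complete, the contrast Lumason® (sulfur hexafluoride lipid type-A microspheres) will be administered through an already existing IV catheter". The trigger is the end of the scan; a finished report is not mentioned. Section 6.3 says that after the study procedure patients "return to the ED (Emergency Department) or floor while they await the results of their gray-scale ultrasound and CT, if one was obtained". Section 17.1 has a parallel sentence: "patients will return to the ED while the results of their gray scale ultrasound and CT, if one was taken, are obtained".

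**Who is present.** Section 6.3: "Lumason will be administered by radiology personnel (radiologist, US technologist, or Sedation RN". A radiologist is thus one of three roles that may inject.

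**Blinding.** Section 6.2: "The CEUS image will be read at a future time by a CMH radiologist blinded to the results of the gray scale ultrasound and CT" (where a CT exists). Section 20.1, on the single radiologist who evaluates the CEUS images: "This radiologist will be blinded to the final reads from the gray scale reports". Section 4.1 also calls the interpreting radiologist blinded. I found no other provision on reader blinding.

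**Role of the gray-scale read.** Section 6.2 says the gray-scale and CT results serve for comparison. Section 20.1 sets the CEUS images against the standard gray-scale report.

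**Use of the images in care.** Section 6.1, on the current diagnostic pathway: "Our study does not look to alter that process". Section 18.1, on possible benefit: "it is possible that the improved quality of US images produced will provide better information to providers treating these patients".

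**The concern.** In a paired imaging comparison each read should be made without knowledge of the other. Here one direction is covered and the other is not. The radiologist who reports gray scale is not blinded to the CEUS. The gray-scale findings need not be recorded before contrast, and access to the CEUS clips is not ordered in any way.

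If a gray-scale report is written with the CEUS in view, a finding that only CEUS made clear can be credited to gray scale. Two things follow:

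- The measured difference between the modalities shrinks, because the comparator already contains part of the gain.
- Membership of the gray-scale-inconclusive group changes. Section 2.2 states the hypothesis for exactly these children. Section 25.1 requires permission/assent before the gray-scale scan, so the group is formed after enrollment and from the gray-scale result. The children most likely to drop out of it are those whom CEUS resolved.

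Read order is fixed when the images are acquired and reported, so it belongs in the protocol's procedures and should not be left to an analysis plan.

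**Working it through.** The protocol gives no figure on this point, so there is nothing to reproduce. The check is of the text.

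**1. Is the gray-scale read required before the CEUS?** No. Section 6.2 ties contrast to completion of the scan. Sections 6.3 and 17.1 both describe the gray-scale result as outstanding after the CEUS. No sentence requires an earlier read, and none forbids one.

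**2. Who is blinded to what?**

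| Reader | Blinded to | Source |
|---|---|---|
| CEUS reader | gray-scale and CT results | 6.2 |
| CEUS reader | gray-scale final reads | 20.1 |
| CEUS reader | not specified | 4.1 |
| Gray-scale reader | nothing stated | – |

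**3. Is there a route for CEUS information to reach the gray-scale reader?** Yes, a possible one. The formal CEUS read is deferred, so no CEUS report exists when the gray-scale report is written. What can leak is sight of the clips, or the impression of someone present at the scan. Deferring the read blocks neither. A radiologist may inject (6.3), and no section says that this is someone other than the reporting radiologist.

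**4. Does the unprotected read matter to the results?** Yes. It is the named comparator (6.2, 20.1), and its conclusive or inconclusive status defines the group in section 2.2.

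**5. Size.** It cannot be derived, because the documents give neither the true share of enhanced images nor any rate of leakage. The following shows sensitivity under assumptions and is not an estimate. Assume one evaluable image set for each of the 250 children, a true share *p* enhanced, and a fraction *f* of that gain absorbed into the gray-scale read and lost from the enhancement count. The observed share is *p*(1 − *f*). The section 4.1 rule of more than 50% then needs at least 126 of 250, and the chance of meeting it is P(X ≥ 126) with X ~ Binomial(250, *p*(1 − *f*)).

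| Assumed *p* | *f* = 0 | *f* = 0.10 | *f* = 0.20 |
|---|---|---|---|
| 0.55 | 0.936 (share 0.55) | 0.412 (0.495) | 0.024 (0.44) |
| 0.60 | 0.999 (0.60) | 0.886 (0.54) | 0.243 (0.48) |
| 0.70 | about 1.00 (0.70) | about 1.00 (0.63) | 0.967 (0.56) |

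Under these assumptions leakage matters to the pass rule when the true share is near 50%, and hardly at all when it is well above.

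**The case against.** **The text does not fix read order.** Sections 6.3 and 17.1 say where the patient waits and what is still pending. They do not say when the radiologist reads. The same sentences also speak of awaiting CT, which under section 6.1 may be requested once gray scale is inconclusive, so a child awaiting CT may already have a gray-scale read. This stands. A reader might infer that every gray-scale report is issued after the CEUS; the protocol does not say so. What remains is that nothing secures an earlier or unexposed read.

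**The route is a chain of possibilities.** A radiologist may inject, may be the one who reports, and may form a view from clips that have had no formal read. This also stands: exposure is possible, not shown.

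**The bias is conservative.** Absorption into the comparator would mostly make CEUS look less useful, so it would not readily create a false claim of benefit. That lowers the severity. It does not remove the point, since a real gain could be understated and the inconclusive group would still be misclassified.

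**The CEUS reader's own blinding.** One might infer that this reader could be the radiologist who reported the same child's gray scale. Sections 6.2 and 20.1 largely close that, because whoever wrote the report cannot be blinded to it. What stays open is narrower: neither section says that having attended the scan counts as a breach.

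**Section 18.1.** It speaks of a possibility and of treating providers. It does not show that the gray-scale reader will see the CEUS. It shows only that the images are not described as withheld from clinical staff.

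**Repair afterwards.** If the pre-contrast images are stored separately, a reader blinded to CEUS could re-read them. So the leak is not irreversible, although the protocol plans no such re-read.

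**Conclusion.** The point holds in a limited form. The protocol blinds the CEUS reader to gray scale and CT but leaves the gray-scale comparator unprotected from the CEUS, while describing the gray-scale result as still awaited after the CEUS is done. The comparator may therefore absorb CEUS information. The likely direction is toward a smaller measured gain, with some change in who counts as inconclusive.

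The size is unknown. The conclusion rests on the absence of any ordering or access rule; it assumes no particular leakage rate.

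A reader might go further and infer that leakage would cost the trial its result of more than 50%. The documents do not support that. The section 4.1 rule concerns enhancement counted in images, as judged by the blinded radiologist. It is not a threshold for the share of inconclusive children whom CEUS resolves, and no threshold is set for that share. How far a contaminated gray-scale read would carry into the enhancement count is itself an assumption.

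This should be fixed as a cheap improvement; it is not a flaw that invalidates the design.

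**What to change.** **Section 6.2.** Require the gray-scale findings (appendix seen, criteria met, conclusive or inconclusive) to be entered in REDCap with a time stamp, from the pre-contrast images, before the reporting radiologist views the CEUS clips. Name that entry as the comparator. Where the order was not kept, flag the case and repeat the result without the flagged cases.

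**Section 20.1.** State that blinding to gray scale means the CEUS reader neither reported nor attended that child's scan, and flag exceptions.

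**Cost.** One short form and an ordering rule for viewing images. REDCap is already in use (6.4). The rule governs only the order of viewing, so the clips need not be withheld once the entry is made, and the possibility of acting on incidental findings (18.1) is untouched. With a single CEUS reader and enrollment at all hours (revision 03), some exceptions are likely. That is why the proposal is to flag them and not to forbid them.

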## 11.0 Inclusion and Exclusion Criteria

### Inclusion Criteria

- Present to Children's Mercy Adele Hall campus with a clinical concern for acute appendicitis
- Age 8 through 17 years
- seen between IRB approval date and 12/31/2020
- Has had an IV catheter placed as part of their standard of care

Exclusion Criteria

- Known cardiac abnormality
- Pulmonary hypertension
- Known sensitivity to sulfur hexafluoride, polyethylene glycol 4000, distearoylphosphatidylcholine (DSPC), dipalmitoylphosphatidylglycerol sodium (DPPG-Na), or palmitic acid
- Does not have an IV catheter placed
- Unable to roll over
- Unable to assent
- Pregnant
- Lactating
- Received an ultrasound image from an OSH

*11.1 These patients will be excluded from the study*

- Adults unable to consent
- Pregnant women
- Prisoners
- Wards of the state

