## 21.0 Provisions to Monitor the Data to Ensure the Safety of Subjects

This study proposes a one-time intervention of CEUS. Subjects will be monitored in real time at the time of and following the CEUS. Data collected will be evaluated after the first 10 subjects are enrolled.

- All data collected on subjects who receive study drug will be analyzed for safety. The proportion of patients with specific adverse events will be reported as well as the worst grade observed across all adverse events. The maximum confidence interval width for these estimates is 16.8%. If the observed estimated adverse event proportion is 10%, the 95% confidence interval is (5.3,15.6%).
- Safety information will be collected at the time of study visit when the patient is monitored during contrast administration.
- Safety data collection will begin with the first participant. Participants will be monitored in real time.
- The PI or an assigned co-investigator will be responsible for monitoring the data.
- Cumulative data will be reviewed on a weekly basis beginning with the first study participant.
- All data collected on subjects who receive study drug will be analyzed for safety. The proportion of patients with specific adverse events will be reported as well as the worst grade observed across all adverse events. The maximum confidence interval width for these estimates is 16.8%. If the observed estimated adverse event proportion is 10%, the 95% confidence interval is (5.3,15.6%).
- Any adverse event resulting from the contrast agent requiring an ICU admission will trigger an immediate suspension of the research.

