## **23.0 Compensation for Research-Related Injury**

23.1 Regular clinical review will minimize the risk of complications or harm as a result of study participation. In the event that an adverse event results from the study procedure, it will be reviewed by the principal investigator, reported to the IRB, and dealt with per institutional policy. Treatment will be available at CMH and will be provided at the usual charge. Payment for this treatment will be the participant's responsibility as this research study does not have funds set aside to pay research participants if the research results in harm or complications. The approved IRB P/A will include known possible adverse events of study participation as well as payment responsibility for any adverse event.

23.2 N/A.

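### No symptom status is planned before the Lumason injection, so nausea already present may be counted in the adverse-event proportion and that proportion cannot be attributed to the contrast

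*Protocol*

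**What the plan says.** All references are to the protocol.

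- **Population (section 11.0).** The first inclusion criterion is "Present to Children's Mercy Adele Hall campus with a clinical concern for acute appendicitis".
- **Symptoms recorded (6.4).** "Reports of headache, nausea, altered taste, injection site reaction, feeling hot/ flushed, chest pain, or dizziness will also be recorded". The sentence has no condition on onset, change or cause.
- **Other data points (6.4).** The list opens with "Data points to be collected include the following: demographics, findings on radiology imaging (US, CEUS, and CT if applicable" and goes on to pathology, intraoperative findings and a comments field. Presenting or pre-injection symptoms are not on it.
- **Timing (21).** "Safety information will be collected at the time of study visit when the patient is monitored during contrast administration". After the procedure, section 6.3 adds that "ED/ floor staff will continue to monitor patients for any adverse events", with no stated end.
- **Analysis (21).** "The proportion of patients with specific adverse events will be reported as well as the worst grade observed across all adverse events".
- **Comparator (6.1, 6.2).** None. The trial is non-randomized and every consenting child is to have one contrast scan.

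**The concern.** The symptom list closely follows the table of reported Lumason reactions in section 17.1, so its purpose is evidently to capture contrast reactions. At least one item on it, nausea, is also a plausible complaint of a child with suspected appendicitis before any contrast is given. Without a comparison group, the child's own state just before injection is the only reference that could separate the two. The protocol does not plan to record it.

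The nausea proportion is at stake, and with it the worst grade, since nausea of long standing could supply that grade. The error can go either way: old nausea may be put down to contrast, or new nausea may be dismissed as part of the illness. The weekly cumulative review in section 21 would look at the same mixture.

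**Working it through.** **1. The plan's own figures.** The concern rests on no stated number. The only figures given for the safety proportions are in section 21: a maximum interval width of 16.8%, and (5.3, 15.6%) at an observed 10%. They do not reproduce at 250 subjects. The Wald width at 50% is 2 × 1.96 × √(0.5 × 0.5 / 250) = 12.4%, and the Clopper-Pearson width is 12.7%. That is a separate matter. Any such interval expresses sampling error only and says nothing about whether the counted events were new.

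**2. Is there a baseline anywhere?**

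- The data points in 6.4 name none.
- Collection under section 21 is tied to contrast administration. This fixes when symptoms are noted, not whether they are new.
- Section 14.4 records the pediatric appendicitis score (PAS), but on a pre-screening log. The log is kept to track enrollment and is destroyed at study end. The protocol does not describe the score as a symptom record or list it among the study data.
- Section 10.0 says standard-of-care data come from the chart. The chart may mention presenting symptoms, but nothing requires them to be extracted, or to be noted item by item just before injection.

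**3. Is there a rule on cause?** Causal wording occurs in two places. The suspension rule in section 21 reads "Any adverse event resulting from the contrast agent requiring an ICU admission will trigger an immediate suspension of the research". Section 23.1 reads "In the event that an adverse event results from the study procedure, it will be reviewed by the principal investigator". Neither governs the proportions that section 21 reports.

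**4. What could the effect be?** Let *b* be the share of children nauseated before injection, *c* the share of those children who are counted, and *d* the rate of new nausea among the rest.

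Recorded children = 250 × [*c* × *b* + (1 − *b*) × *d*]

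For *d* take 0.5% from section 17.1. Neither *b* nor *c* is in the protocol, so both are assumptions, shown over a range.

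| *b* | *c* = 0 | *c* = 0.1 | *c* = 0.5 | *c* = 1 |
|---|---|---|---|---|
| 10% | 1.1 | 3.6 | 13.6 | 26.1 |
| 30% | 0.9 | 8.4 | 38.4 | 75.9 |
| 50% | 0.6 | 13.1 | 63.1 | 125.6 |

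Example: *b* = 30%, *c* = 0.1 gives 250 × (0.03 + 0.7 × 0.005) = 250 × 0.0335 = 8.4.

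The first column is what a count of new nausea only would give. The last is the worst case, in which every nauseated child is counted. The spread shows that the size cannot be settled from the protocol. One statement needs neither *b* nor *c*: 0.005 × 250 = 1.25, so two miscounted children (2/250 = 0.8%) already exceed the whole number expected at the reference rate.

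**The case against.** A reader might infer that presenting nausea is certain to be counted as a Lumason adverse event. The protocol does not say that. Section 6.4 says reports are recorded. Section 21 summarises adverse events in subjects who received study drug and ties collection to contrast administration. The two causal phrases show that attribution was in mind. This stands: the supportable word is *may*.

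A reader might also turn an assumed prevalence of nausea into a large multiple of the section 17.1 rate. That would rest on a figure the protocol does not give and on the worst-case column above. The protocol also plans no comparison with section 17.1, whose table is risk disclosure. This stands too.

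Three further points limit the matter. Safety is not a named objective or endpoint in sections 1.0, 2.0 or 4.0. The suspension rule depends on an ICU admission caused by contrast, so miscounted nausea would not trigger it. The overlap is clear only for nausea, arguable for headache and feeling hot, and not shown for the other items.

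The remaining defence is that the analysis plan or the REDCap form, neither of which is shown, may deal with it. A definition of new or worsened events could well sit in the analysis plan. It would still need a pre-injection observation to work on, and the protocol's data list names none. That list is worded as what data points include, so a form could go further, but nothing in the text requires it. Chart notes give at best a partial substitute, taken at another time and without severity for each symptom.

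**Conclusion.** The point holds in limited form. The protocol sets a symptom list that overlaps with the presenting illness, reports proportions from it with no condition that a symptom be new or worse, names no pre-injection status, and has no control group. Pre-existing nausea may therefore be counted, and the reported proportion cannot be attributed to Lumason. The same may apply, less clearly, to headache and feeling hot.

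The size is unknown. It depends on how many children are nauseated before injection and how many of them are counted, and the protocol gives neither. That nausea accompanies suspected appendicitis is general clinical knowledge and is not stated in the protocol. The diagnostic endpoints and the suspension rule are unaffected. The gap should be closed because it lies in data collection and cannot be fully repaired at analysis.

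**What to change.** - **Section 6.4:** add that presence and severity of each listed symptom are recorded immediately before the Lumason injection.
- **Section 21:** state that the adverse-event proportion and worst grade count only symptoms that are new or have worsened since that record, and that pre-existing symptoms are listed separately.

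The cost is one added REDCap form, about one minute per child at the bedside, and the amendment wording. For any child already scanned, only chart notes can serve as a baseline, and the report should say so.
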